Vagus Nerve Stimulation as Treatment for Long Covid PI: [name] NCT05608629 Document Date: 3/8/2022

PROTOCOL for Vagus Nerve Stimulation as a Treatment of Long Covid

A surprisingly large number of patients who have survived COVID infection remain ill with a syndrome commonly called Long Covid. A report from this institution¹ reported that the most common symptoms following the acute infection were fatigue, brain fog and headache. Our own work confirmed our hypothesis that many of these patients were so severely ill that they fulfilled case criteria for chronic fatigue syndrome [Mancini et al and Natelson, in press]. There is no current treatment and so physicians in practice have little they can offer such patients. Importantly, a recent paper used vagus nerve stimulation [VNS] via electrodes attached to the left tragus and reported improvement in a number of symptoms of Long Covid². Since cervical VNS is known to downregulate immune function and is currently being tested as a treatment for rheumatoid arthritis, the researchers had hypothesized that improvement might be due to immune downregulation³; however there was no evidence of immune dysregulation prior to treatment and thus the hypothesis could not be tested. Although the mechanism for improvement remains unknown, the important thing was that auricular VNS did improve the health status of patients with Long Covid – a condition for which alternative therapies do not exist.

[name] has extensive experience with using VNS to treat medically unexplained symptoms. In the first study, the only way to chronically stimulate the vagus was via an implanted stimulator surgically inserted around the left cervical vagus⁴. The study was done on 13 women with fibromyalgia – a pain syndrome associated with substantial fatigue. That study was important for two reasons: First implanted subjects were able to tolerate stimulation usually in most cases without problems and second, five of the patients no longer fulfilled criteria for fibromyalgia at the end of the study – an outcome never reported in any previous drug study. A major problem with this study was its expense – the cost for surgery and device exceeded \$25,000.

Unfortunately, efforts to get NIH funding for a blinded follow up study were unsuccessful. Therefore, [name] applied for and got funding to use VNS to try to reduce the widespread pain reported by many Gulf War veterans using transcutaneous VNS to the left vagus. Unfortunately, the results of that study were negative⁵. We believe the reason for this lack of effect was that the amount of stimulation in the tVNS study was only 12 min while that for the implanted VNS study was 144 min. Fortunately, the device used in the study on Long Covid clipped to the tragus of the ear and allowed stimulation for 35 min a day over the 10 days of study. We believe the difference in outcome between our own Gulf Vet study and this one on Long Covid has to do with amount of stimulation delivered and the fact that auricular VNS targets afferent fibers only while cervical VNS activates both afferent and efferent fibers. We propose using the same device used in the Long Covid study here. Importantly the transcutaneous device that stimulates the auricular branch of the vagus has been designated non-significant risk (NSR) by the FDA [This designation was given in the process of US regulatory work by the manufacturer]. Therefore this proposed trial will not require any interaction with FDA.

This will be an investigator-initiated pilot study seeking evaluable data on 15 subjects; we are asking the IRB permission to enroll up to 18 subjects in case of drop out. If the outcome is positive, [name] will immediately use the results to write an RO1 to do a blinded trial of VNS in Long Covid.

Effective Date: 3/8/2022 End Date:3/7/2023

ResearchMatch will be used as a method for identifying and contacting potential subjects. The study specific announcement is included with this submission.

Inclusion Criteria

- Patient had a history compatible with COVID-19 infection at least 6 months previous to today.
- Patient was not admitted to an ICU and did not require oxygen supplementation if hospitalized
- Patient did not have organ pathology during COVID-19 such as pneumonia.
- Patient has been cleared by primary care provider or specialist as having no medical explanation for their symptoms and signs and has had a recent normal ECG (within 4 months).
- Patient continues ill and identifies his/her major problem as being one with fatigue, brain fog or widespread pain. To be included in the study, the patient must have at least one of the following: fatigue sufficient to produce a substantial decrease in activity at work, home, social or school life over the past month where substantial is 3 or higher on a 0 to 5 scale [0, none; 1, mild; 2, moderate; 3, substantial; 4, severe; 5, very severe]; brain fog producing at least a substantial burden over the past month; four quadrant pain producing at least a substantial burden over the past month.
- Sexually active women will be asked to take at home pregnancy tests if willing to participate in this trial. Pregnancy tests will be reimbursed and patients will communicate with the coordinator the results as well as show proof. We will not be testing menopausal woman or women without a sexual partner.
- Patient is 18 to 72 [upper age limit to exclude older patients who may have cover disease producing their symptoms].

Patients will sign informed consent remotely via RedCap. Patients will already have been seen by a physician who will have ruled out any medical cause for the patient's current symptoms. Patients will complete the Chalder Fatigue Scale [11 questions with four possible answers each]; Short Profile of Mood States [37 words concerning which patients provide input on a 5 point scale ranging from not at all to extremely] and the SF-36, a 36 question vehicle to determine the patient's health related quality of life.

The Parasym - The study team will store and dispense the investigational device with the appropriate guidance. The investigational device will be stored with the Principal Investigator within a locked cabinet in a locked room. Upon receipt of investigational device, inventory the shipment, insuring that information on all packing slips (inside and outside containers) matches exactly the contents of the containers including: Quantity, Lot numbers, Quantity per dispensing package. Insure the device and supplies required for study conduct are within an appropriate expiration date - record receipt. Dispensing of Investigational device - Each time study article is dispensed by the Investigator or other member of the research team, the Study Device Dispensing Log will be completed. All investigation devices dispense will include the following labeling: The investigational device or its immediate package shall bear a label with the following information: the name and place of business of the manufacturer, packer, or distributor the quantity of contents, if appropriate, and the following statement: "CAUTION--Investigational device. Limited by Federal (or United States) law to investigational use." The label or other

Effective Date: 3/8/2022 End Date:3/7/2023 labeling shall describe all relevant contraindications, hazards, adverse effects, interfering substances or devices, warnings, and precautions. Documentation on these forms will include: Date of dispensing, Subject's identifying number and/or initials, Lot number(s), Name or initials of individual dispensing, Date/time study device returned by subject • Subject who returned device identified by number and/or initials. After use by the subject, accept and retain all returned, used study devices and store in a locked cabinet in a locked room only accessible by the study team. If the device is missing, document the reasons.

Disposal Parasym – the study article is prepared for return to supplier or disposed of on-site. File copies of study device packing slips, shipment receipts, accountability records, and disposal instructions appropriately. Note return or disposal on the Dispensing Log. Patients that complete the trial will be able to keep the device, those who opt out of the trial prior to completion will have to return the device. This will be written in the dispensing log.

They will then be mailed a Parasym device and have a zoom session with research personnel to assure appropriate use. Subjects will be instructed to use the device as instructed [i.e., attached to the left tragus] for 35 min each day using a current which is not uncomfortable to use. That is, subjects can adjust the current and will asked to increase it to an intensity that is tolerable to use for the 35 min stimulation period. Patient will be able to control the duration of the stimulus. We will advise the subject to give him/herself at least 35 min of stimulation but that they can increase that duration up to an hour pending how they feel [the study on Long COVID used 35 min but in their other trials, they use 60 min].

Patients will be provided the cell number of a member of the research team and will be told to call if they have any problems or questions about the treatment or the study itself.

Patients will be called at 4 and 6 weeks after starting treatment and will again be asked to provide data on the visual analog scales concerning [1] fatigue; [2] brain fog; [3] widespread pain. They will also be asked to complete the Chalder, POMS, the SF-36 and a 7 point question on self rated current state of health [+3 very much better; 0 no change; -3 very much worse] -- Patient Global Impression of Change (PGIC).

Criteria for primary outcome: Improvement on two of the following with improvement defined as: a 0.6 SD reduction in impaired physical function on the SF-36; reduction in severity of the most troubling symptom endorsed by the patient to 0-2 on the visual analog scale [none, mild or moderate]; no longer a "case" on the Chalder; much improved or very much improved on the PGIC.

Criterion for secondary outcome: Improvement by at least 10 points on the short version of the POMS.

Criteria for successful outcome: At least a third of patients fulfill criteria for primary outcome.

At the conclusion of the study, patients will be able to keep their Parasym VNS device.

Effective Date: 3/8/2022 End Date:3/7/2023

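### Does the one-third success bar fail because it does not say whether drop-outs count in the denominator?

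*Protocol*

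**What the plan says.** The Protocol has no numbered sections. The design paragraph before Inclusion Criteria gives the only sizing statement: the pilot is "seeking evaluable data on 15 subjects; we are asking the IRB permission to enroll up to 18 subjects in case of drop out". Near the end, under the criteria for a successful outcome, the trial-level bar reads "At least a third of patients fulfill criteria for primary outcome". A patient meets the primary outcome by improving on two of four components: SF-36 physical function, the most troubling symptom, Chalder caseness and the PGIC.

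Outcome data come from follow-up contacts: "Patients will be called at 4 and 6 weeks after starting treatment". For people who leave early, the text on device disposal says only that "those who opt out of the trial prior to completion will have to return the device". Nothing defines an evaluable patient, and nothing says how a patient without outcome data counts towards the bar. The stated consequence of a positive result is that the investigator "will immediately use the results to write an RO1 to do a blinded trial of VNS in Long Covid".

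**The concern.** A proportion needs a denominator, and the success rule names none. The Protocol expects drop-out and allows three extra enrolments for it, so the evaluable count and the all-started count may differ. No control arm is described and all four components of the primary outcome are patient-reported. If no other document settles the matter, the denominator could be chosen after the number of responders is known.

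Patients who find the device unhelpful may also be the ones who leave. A rate among completers would then be too high, and a weak result could be called positive and carried into a grant application.

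**Working it through.** **Inputs.** From the design paragraph: 15 evaluable and at most 18 enrolled. From the success criterion: a bar of 1/3. The Protocol gives no drop-out rate, null rate, significance level or power, so there is no sample-size figure to reproduce. As a consistency check, 15 evaluable with 3 of 18 lost gives 15/(1 − 3/18) = 18, which matches the cap. All true responder rates below are assumptions.

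**Step 1: responders needed.** The minimum is n/3 rounded up.

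| Denominator n | Responders needed | 5/n |
|---|---|---|
| 12 | 4 | 41.7% |
| 13 | 5 | 38.5% |
| 14 | 5 | 35.7% |
| 15 | 5 | 33.3% |
| 16 | 6 | 31.3% |
| 17 | 6 | 29.4% |
| 18 | 6 | 27.8% |

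**Step 2: where the two readings disagree.**
- 13 to 15 evaluable, 16 to 18 started: only at exactly 5 responders.
- 12 evaluable, 16 to 18 started: at 4 and at 5.
- 12 evaluable, 15 started: at 4 only.
- 13 or 14 evaluable, 15 started: nowhere.
- No drop-outs: nowhere.

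The cap of 18 is on enrolment. Consent and baseline questionnaires come before the device is mailed, so some drop-outs may never stimulate. They would not enter an all-started denominator.

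**Step 3: drop-out unrelated to response.** Take 15 completers with responder rate p, so X ~ Bin(15, p). The evaluable reading needs X ≥ 5. The all-started reading with missing as failure needs X ≥ 6, whether 1, 2 or 3 dropped out. The gap is P(X = 5).

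| Assumed p | P(X ≥ 5) | P(X ≥ 6) | P(X = 5) |
|---|---|---|---|
| 0.20 | 16.4% | 6.1% | 10.3% |
| 0.25 | 31.4% | 14.8% | 16.5% |
| 0.30 | 48.5% | 27.8% | 20.6% |
| 1/3 | 59.6% | 38.2% | 21.4% |
| 0.40 | 78.3% | 59.7% | 18.6% |

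Here the completers' rate is unbiased and the all-started rate is too low. With 3 drop-outs a true 25% is reported on average as 0.25 × 15/18 = 20.8%.

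**Step 4: every drop-out a non-responder.** With 18 started, 3 drop-outs and rate p among all started, compare P(Bin(18, p) ≥ 5) for the evaluable reading with P(Bin(18, p) ≥ 6) for the all-started reading. The results are 28.4% against 13.3% at p = 0.20, and 48.1% against 28.3% at p = 0.25. Here the evaluable rate is too high, by a factor of at most 18/15 = 1.2.

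**Step 5: what the disputed count can tell anyone.** The exact 95% interval is 11.8% to 61.6% for 5/15 and 9.7% to 53.5% for 5/18. The two results carry nearly the same information about the response rate, although one passes and the other fails.

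**The case for a change.** The strongest case for a change is that the Protocol did not defer its decision rule. It wrote the threshold itself and left the denominator out, so the criterion is incomplete as it stands. When the true rate is close to the bar, the disputed count of 5 among 15 completers occurs in about one trial in five (21.4% at one third). Naming the denominator would need a few words and no extra patients or data, and it would remove a choice that might otherwise be made with the result in view.

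The ambiguity and the arithmetic stand. The conclusion does not. A protocol that states a bar and leaves its analysis set to a statistical analysis plan follows ordinary practice, and a late choice is possible only if no such plan fixes the set. Nothing in the success criterion is false or contradicted elsewhere. The sizing sentence also largely answers the question, because it seeks a number of evaluable patients and enrols extra people to reach it.

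That leaves a preference for counting missing patients as failures among all who start. It protects against drop-out related to poor response (Step 4), but it biases the rate downwards and discards promising results when drop-out is unrelated (Step 3). The Protocol gives no basis for deciding which situation applies.

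**Conclusion.** No change to the plan follows. This is an unstated analysis detail of a kind that analysts settle sensibly, and the one substantive alternative is a fair trade-off rather than a correction.

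With 13 to 15 evaluable and 16 to 18 started, the choice of denominator alters the verdict only at exactly 5 responders. With 15 completers, that count has a probability of 10.3% to 21.4% for assumed rates from 20% to 40%. With 12 evaluable of 16 to 18 started, 4 and 5 are both open. If all drop-outs happen before stimulation, an all-started count raises no dispute. The largest overstatement is 1.2-fold, and it needs 15 evaluable of 18 started with no responder among the drop-outs.

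The stakes are limited: this is an uncontrolled pilot with no stated hypothesis test, and its stated next step is an application for a blinded trial. A report giving the rate among all who started and among the evaluable, with the numbers started, dropped out and evaluable, lets any reader apply either denominator. The conclusion assumes that the unseen analysis plan, or the analysts, will name the denominator before responders are counted. Doing so in the success criterion would be a harmless clarification.

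### The scheduled week-4 and week-6 calls list no question on adverse events, so harms of self-adjusted home stimulation are likely to be under-counted

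*Protocol*

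**What the plan says.** The protocol has few headings, so places are given by content.

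- **Treatment.** "They will then be mailed a Parasym device and have a zoom session with research personnel to assure appropriate use". Sessions are then done at home. On intensity, "subjects can adjust the current and will asked to increase it to an intensity that is tolerable to use". Duration is also under the patient's control, from 35 minutes up to an hour a day.
- **Problems.** Patients receive a team member's phone number and "will be told to call if they have any problems or questions about the treatment or the study itself".
- **Follow-up.** "Patients will be called at 4 and 6 weeks after starting treatment". At those calls they are "asked to provide data on the visual analog scales concerning [1] fatigue; [2] brain fog; [3] widespread pain". The next sentence completes the list: "They will also be asked to complete the Chalder, POMS, the SF-36 and a 7 point question on self rated current state of health". That last item is the global impression of change, which runs from +3 down to -3, very much worse.
- **Device storage, dispensing and disposal.** The labelling clause ("labeling shall describe all relevant contraindications, hazards, adverse effects") concerns what the user is told. The dispensing log records dates, identifiers and lot numbers. Reasons are documented only when a device is missing.
- **Size and purpose.** The pilot seeks 15 evaluable subjects and may enrol up to 18. A positive outcome is to be used at once for a grant application for a blinded trial.

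**The concern.** The text names one way for a problem to reach the study team, and it depends on the patient taking the initiative. It also sets out what is collected when staff take the initiative, and that list contains no question on harms. Followed as written, the harms record would rest on what patients choose to volunteer. A mild, gradual or embarrassing effect is the kind least likely to prompt a call.

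A patient who stops because of discomfort must return the device, but the log does not ask why the patient stopped. The patients with the most informative experience could leave no record of it.

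The protocol's background names tolerability as one of two reasons why the earlier implanted-stimulator study mattered. This pilot would have no systematic data for a similar statement. Exposure may also be well above that of the cited Long Covid study, which the protocol gives as 35 minutes a day for 10 days, or 350 minutes. Daily use up to the week-6 call (an assumption, since no end of treatment is stated) gives 42 × 35 = 1,470 to 42 × 60 = 2,520 minutes, about 4 to 7 times as much. Tolerability there cannot simply be carried over.

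**Working it through.** **Reading the text.** The protocol gives no adverse event rate, safety target or safety calculation, so there is no figure to reproduce. The check is what each contact or record collects.

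| Contact or record | Started by | Harms content stated |
|---|---|---|
| Phone number | Patient | Any problem or question |
| Week-4 and week-6 calls | Staff | None; symptom scales, Chalder, POMS, SF-36, global impression |
| Dispensing log | Staff | None; device accountability |
| Device label | Manufacturer or study | Informs the user, collects nothing |

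No paragraph defines an adverse event, a harms form or a safety outcome.

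**Illustration of size.** Inputs:
- n = 15 (evaluable target) and n = 18 (maximum enrolment), both from the protocol.
- p = true share of patients with a given event. Assumed: 10%, with 5% and 20% as a range.
- r = share of affected patients whose event reaches the team. Assumed: 1 if everyone is asked (an idealisation), and 0.5 or 0.25 under volunteered reporting.

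Chance of recording at least one event: 1 − (1 − p·r)^n.

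For p = 10%, n = 15:
- r = 1: 1 − 0.90^15 = 0.794
- r = 0.5: 1 − 0.95^15 = 0.537
- r = 0.25: 1 − 0.975^15 = 0.316

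| p | n | r = 1 | r = 0.5 | r = 0.25 |
|---|---|---|---|---|
| 5% | 15 | 54% | 32% | 17% |
| 5% | 18 | 60% | 37% | 20% |
| 10% | 15 | 79% | 54% | 32% |
| 10% | 18 | 85% | 60% | 37% |
| 20% | 15 | 96% | 79% | 54% |
| 20% | 18 | 98% | 85% | 60% |

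**If no event is recorded.** The two-sided 95% upper limit is 1 − 0.025^(1/n):
- n = 15: 0.218, or 22%
- n = 18: 0.185, or 18.5%

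This bounds the rate of *recorded* events. It bounds the true rate only if every patient was asked. If a fraction r of affected patients report, the matching limit on the true rate is the figure above divided by r. At r = 0.5 that is 0.218/0.5 = 44% for 15 patients and 0.185/0.5 = 37% for 18.

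**The case against.** The strongest reply is that this turns silence into a rule. The phone number reads as a support line. The text does not say that harms are recorded only that way, and the list of call content does not say it is complete. Consent pages are not shown, and other parts of the ethics submission cannot be seen. The reference list even includes a paper on vagus nerve stimulation in pregnancy that no visible text cites. That is consistent with safety wording elsewhere, though a leftover reference is equally possible.

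This part stands. A reader might infer that no harms will be captured unless a patient phones in, or that the study has no adverse event procedure at all. The document supports neither. It supports only the statement that no solicited collection appears in the text shown.

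It is also fair that everyone is asked about overall worsening through the symptom scales, SF-36, POMS and the global impression, and that patients may volunteer events during a call. This softens the concern but does not remove it. None of those scales separates a device effect from the course of the illness, and nothing tells staff to record what is volunteered.

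Two further replies carry less weight. The protocol sets no safety objective, and it describes the device as designated non-significant risk. The first limits how serious the gap is. The second is a regulatory classification and does not replace measurement. Nor is this a matter for the analysis plan, which cannot analyse data that were never collected.

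**Conclusion.** The point holds in a limited form. In the text shown, the only stated route for reporting problems is patient-initiated, and the two itemised staff calls carry no harms question. Adverse events are therefore likely to be under-counted. The direction is a sound inference from reliance on volunteered reports, but the size is unknown, because the protocol gives neither an event risk nor a reporting fraction. The drop from 79% to 54% or 32% (15 patients), or from 85% to 60% or 37% (18 users), shows what the assumed 10% risk and assumed fractions would imply. It is not an estimate for this trial.

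A reader might go further and conclude that events will certainly be missed, or that home stimulation here is unsafe. The document supports neither conclusion. What would be lost is the ability to interpret a low or zero event count.

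**What to change.** - At the week-4 and week-6 calls, add one open question on new or worsened problems since the last contact, then a short checklist of the effects named on the device label.
- Ask the same of anyone who withdraws, at that contact or when the device is returned.
- Record onset, severity and relation to the device on a form.
- Report the number of patients with each event over all who used the device (up to 18), not only the 15 evaluable. Show solicited and phoned-in events separately.
- Keep the call-in number.

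If such a procedure already exists elsewhere in the submission, a cross-reference in the follow-up paragraph is enough.

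The cost is a few minutes per call, one form and one table, with no added visit. Reported event counts will probably be somewhat higher, because asking finds more than waiting does.

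### The week 4 and 6 symptom ratings, one of four self-reported primary components, are asked for on a call, with no independent caller named and no mode fixed for the other scales

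*Protocol*

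**What the plan says.** For follow-up, the protocol states "Patients will be called at 4 and 6 weeks after starting treatment and will again be asked to provide data on the visual analog scales", and names fatigue, brain fog and widespread pain. The caller is not identified. The next sentence covers the remaining instruments: "They will also be asked to complete the Chalder, POMS, the SF-36 and a 7 point question on self rated current state of health", which is the PGIC. It does not say whether these are answered aloud, on paper or electronically.

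The primary outcome rule begins "Criteria for primary outcome: Improvement on two of the following with improvement defined as: a 0.6 SD reduction in impaired physical function on the SF-36". The other components are "reduction in severity of the most troubling symptom endorsed by the patient to 0-2 on the visual analog scale" and "no longer a 'case' on the Chalder; much improved or very much improved on the PGIC". Success for the study is "At least a third of patients fulfill criteria for primary outcome".

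The introductory section seeks 15 evaluable subjects, allows up to 18 to be enrolled, and defers a blinded trial to a later grant application. No control or sham arm is described. On contact with staff, patients "have a zoom session with research personnel to assure appropriate use" and are given the number of a research team member to ring about problems or questions. On electronic systems the protocol says only "Patients will sign informed consent remotely via RedCap".

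**The concern.** All four primary components are the patient's own judgement, and no objective measure sits beside them. Patients know they are treated. With a single arm, nothing subtracts a general tendency to answer favourably, so any such tendency goes straight into the responder count.

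A rating given aloud to someone connected with the study is more open to courtesy and prompting than one entered alone. The protocol ties the symptom ratings to a call and says nothing to separate the person collecting them from the people who train and support the patient. The step needed can be small. Inclusion Criteria define a qualifying symptom as 3 or higher on a 0 to 5 scale, and the primary component is met at 0 to 2. If the same scale is used at follow-up, as the matching labels suggest, a patient who enters at grade 3 meets the component by moving one grade.

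At stake is how far a positive result can be trusted, since the sponsor plans to use it at once to support a larger trial.

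**Working it through.** **Inputs from the protocol.** Evaluable patients n = 15 (up to 18 enrolled). Responder: at least 2 of 4 components. Success: at least one third responders, which is 15/3 = 5 of 15, or 18/3 = 6 of 18.

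**The plan's own figure.** The protocol states no null rate, target rate, alpha or power, so there is no operating characteristic to reproduce. The one-third threshold is the only decision figure.

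**What each instrument's text fixes at follow-up.**

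| Instrument | Primary component | Tied to the call | Mode stated |
|---|---|---|---|
| Symptom ratings | Yes | Yes | Asked for on the call |
| SF-36 physical function | Yes | Not expressly | None |
| Chalder | Yes | Not expressly | None |
| PGIC | Yes | Not expressly | None |
| POMS | No (secondary) | Not expressly | None |

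A responder needs two components, so a favourable symptom rating changes a patient's status only if that patient meets exactly one of the other three. That limits the route by which this bias acts.

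**Sensitivity of the success rule (rates assumed).** P(X ≥ 5) = 1 − Σ C(15,k) p^k (1−p)^(15−k), summed over k = 0 to 4.

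At p = 0.25 the five terms are 0.0134, 0.0668, 0.1559, 0.2252 and 0.2252. Their sum is 0.6865, so P = 0.314.

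The same formula gives:

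| Observed response rate | P(at least 5 of 15) |
|---|---|
| 20% | 0.164 |
| 25% | 0.314 |
| 30% | 0.485 |
| 35% | 0.648 |
| 40% | 0.783 |

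A move from 25% to 30% is 0.05 × 15 = 0.75 of a patient on average.

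**A second way to express the bias (also assumed).** Let a share m of true non-responders be recorded as responders, so the observed rate is q = p + (1 − p)m.

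- p = 0.20, m = 0.10: q = 0.20 + 0.80 × 0.10 = 0.28. P rises from 0.164 to 0.415 (6 of 18: 0.133 to 0.391).
- p = 0.25, m = 0.10: q = 0.25 + 0.75 × 0.10 = 0.325. P rises from 0.314 to 0.569 (6 of 18: 0.283 to 0.558).

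Both versions show that the success rule is sensitive to one or two extra responders. Neither shows how many extra responders a spoken rating would produce.

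**The case against.** The strongest reply is that the text says less than a reader might infer.

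- **Who calls.** A reader might take the caller to be the unblinded team that trained the patient. The protocol uses the passive and names nobody. The inference is plausible, because no independent assessor is described, but it is not stated.
- **What is spoken.** A reader might infer that every outcome is taken aloud. Only the symptom ratings are tied to the call. The Chalder, POMS and SF-36 together have 11 + 37 + 36 = 84 items by the protocol's own counts, so reading them out is not the natural meaning. The argument that a spoken symptom grade plus a spoken PGIC would alone make a responder needs a mode for the PGIC that the protocol does not give.
- **Change of mode.** A reader might infer that the mode differs before and after treatment. For the questionnaires collected at both times, the text speaks of completing them at both. For the symptom ratings, the word 'again' points to the same approach, and no baseline mode is stated.
- **Keeping the device.** This might look like a reward for good answers. The device-handling section ties it to completing the trial, whatever the patient reports.

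These four objections stand, and the point does not rely on any of those readings. It is also true that expectation and placebo effects are probably the larger problem in an open single-arm pilot, that self-completion does not touch them, and that live collection protects against missing data in a sample of 15. What remains is that one primary component is requested by call, the mode for the other three is open, and nothing separates the collector from the research team. How outcomes are collected is a matter of conduct that the protocol should settle.

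**Conclusion.** The point holds as a modest improvement to conduct. It is not a numerical error and does not invalidate the design. In an uncontrolled study with a threshold of 5 of 15, a symptom rating spoken to staff can turn a patient who meets one other component into a responder.

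The size is unknown. The step from 0.314 to 0.485 for a rise from 25% to 30% rests on an assumed true rate and an assumed lift, and treats patients as independent. It shows how sensitive the rule is and does not estimate the bias. If the sponsor already intends self-completion, one sentence in the protocol closes the point.

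**What to change.** State in the follow-up paragraph that patients complete the three symptom ratings, the PGIC, Chalder, POMS and SF-36 themselves. Use the same mode at every time point at which each is collected, and have the week 4 and week 6 forms completed before the corresponding call. REDCap forms are one option; the protocol documents REDCap only for remote consent, so its use for outcome data would be new. Keep the calls for questions, problems and reminders. Where a patient cannot complete a form, allow the answers to be read out and flag them in the data.

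The cost is a small form build for at most 18 patients, and some late forms that need a reminder. Endpoints, sample size and treatment are unchanged. The report should still say that expectation and placebo effects remain.
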